 - Blood sample for assessment of parasitemia (PCR testing) will be collected on the day of subject entry into the hotel phase (Day 295 [Visit 16]) to provide an estimate of the number of subjects likely to develop malaria within the first few days of the hotel phase.
 - Blood sample for assessment of parasitemia (blood smear) will be collected daily for 14 days (from Day 291 [Visit 12] to Day 304 [Visit 25]) and then every two days for nine days (Day 306 [Visit 26], Day 308 [Visit 27], Day 310 [Visit 28], Day 312 [Visit 29], and Day 314 [Visit 30]). For subjects who develop malaria, blood smear may be discontinued once the subject has three consecutive negative smears (separated by more than 12 hours) following the initial treatment (see Section 6.4.1).
 - Blood samples for testing of HIV, hepatitis C virus (HCV) and HBsAg will be collected from all subjects at screening.
 - Urinary pregnancy test (urine beta-human chorionic gonadotropin [β -HCG]) will be performed on all women at screening, before each vaccine dose for vaccinated subjects and on the day of challenge.
- Type of study: self-contained.
 - Data collection: electronic Case Report Form (eCRF).

- Safety monitoring:
 - Each subject will be observed for at least 30 minutes after vaccination to evaluate and treat any acute AEs.
 - Each subject will be observed for at least 30 minutes following completion of the sporozoite challenge to evaluate and treat any acute allergic reactions.
 - All SAEs (all, fatal, related to the investigational vaccine) and pregnancies will be reported until study end (Day 376).
 - All AEs and SAEs leading to withdrawal from further vaccination will be reported until study end (Day 376) for all vaccinated subjects (AduFx, 2PedFx, PedFx, Adu2Fx, and Adu1Fx groups).
 - Meningitis and pIMDs are AEs of specific interest to be reported until study end (Day 376; see Section 9.1.5) for all vaccinated subjects (AduFx, 2PedFx, PedFx, Adu2Fx, and Adu1Fx groups).
 - Solicited local and general AEs will be collected from all vaccinated subjects (AduFx, 2PedFx, PedFx, Adu2Fx, and Adu1Fx groups) during seven days (day of vaccination and six subsequent days) after each dose of study vaccine.
 - Unsolicited AEs will be collected from all vaccinated subjects (AduFx, 2PedFx, PedFx, Adu2Fx, and Adu1Fx groups) during 30 days (day of vaccination and 29 subsequent days) after each dose of study vaccine.

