During the hotel phase, all challenged subjects will be assessed on a daily basis in an identical manner. An evaluation will be done each morning (headache, muscle aches, etc.) and blood will be drawn for smear. All challenged subjects will be instructed to check in with clinical staff by telephone call or in-person each evening during the hotel stay until they are positive for malaria. They will be asked if they feel any differently since they were seen in the morning. At any time required, the on-duty investigator will arrange for the timely production of blood smears, along with their examination and interpretation, in order to treat rapidly those subjects in whom therapy for malaria is indicated. Once a positive smear is identified, daily blood films will continue to be obtained until three consecutive films are negative (separated by more than 12 hours). A complete blood count and serum chemistry tests will be done when parasites are initially found in the blood (this could be done on the day of parasitemia detection or the day after).

The maximum hotel stay for malaria-challenged subjects should be approximately 10 days (Day 295 [Visit 16] to Day 304 [Visit 25]). A subject who develops malaria, is treated, and has three consecutive negative malaria smears (separated by more than 12 hours), will not need to remain in the hotel. The investigators will be responsible for accounting for any subjects who do not arrive in the hotel during the challenge phase. If required, the investigators will physically locate and treat any malaria-infected subject who is unable to maintain the follow-up dictated by this study.

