If infection does not develop within 18 days, the subject will be released from staying nightly at the hotel. Subjects who do not develop malaria will be required to come to the clinical center for evaluation and blood drawing for smears every two days up to 28 days post-challenge (Days 306 [Visit 26], 308 [Visit 27], 310 [Visit 28], 312 [Visit 29], and 314 [Visit 30]). A subject who develops malaria and has three consecutive (separated by more than 12 hours) negative smears following initial treatment may be excused from the remaining hotel visits and the late post-challenge clinic visits at Days 306, 308, 310, and 312 (20, 22, 24 and 26 days post-challenge), but will be required to come to the clinic center at Day 314 (28 days post-challenge [Visit 30]). Telephone contact will be made if the subject does not keep a scheduled follow-up appointment. Symptom screening via telephone may suffice in lieu of clinical visits for Days 306, 308, 310, or 312 which fall upon a weekend.

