10.2.1. Subject withdrawal from the study

From an analysis perspective, a 'withdrawal' from the study refers to any subject who did not come back for the concluding visit foreseen in the protocol.

All data collected until the date of withdrawal/last contact of the subject will be used for the analysis.

A subject is considered a 'withdrawal' from the study when no study procedure has occurred, no follow-up has been performed and no further information has been collected for this subject from the date of withdrawal/last contact.

Investigators will make an attempt to contact those subjects who do not return for scheduled visits or follow-up.

Information relative to the withdrawal will be documented in the eCRF. The investigator will document whether the decision to withdraw a subject from the study was made by the subject himself/herself, or by the investigator, as well as which of the following possible reasons was responsible for withdrawal:

- SAE.
- Non-SAE.
- Protocol violation (specify).
- Consent withdrawal, not due to an AE*.
- Moved from the study area.
- Lost to follow-up.
- Other (specify).

*In case a subject is withdrawn from the study because he/she has withdrawn consent, the investigator will document the reason for withdrawal of consent, if specified by the subject, in the eCRF.

Subjects who are withdrawn from the study because of SAEs/AEs must be clearly distinguished from subjects who are withdrawn for other reasons. Investigators will follow subjects who are withdrawn from the study as result of a SAE/AE until resolution of the event (see Section 9.5.1.2).

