6.3.2. Additional considerations

6.3.2.1. Case definition

The primary case definition of *P. falciparum* infection is an asexual blood stage *P. falciparum* parasite density > 0 detected by blood slide reading.

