6.3.2.2. Risk periods

For the analyses of time to onset of parasitemia (Kaplan-Meier and Log-Rank), time at risk will start on first day of challenge. Time at risk will be censored on protocol visit D314 (28 days post challenge), drop-out date, start date of antimalarial treatment or date meeting an endpoint, whichever occurs first. Time at risk will be calculated as: censor date – date challenge + 1.

For the analysis of proportion affected (relative risk), all subjects included in the PPS for analysis of immunogenicity and efficacy will be considered at risk of infection and no censoring or elimination will be applied for subjects not completing the entire protocol defined post challenge follow-up (visit D314 - 28 days post challenge).

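### Time to onset is censored at an undefined drop-out date rather than at the last negative blood slide, so days without a slide can count as infection-free in whichever group loses subjects after challenge

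*SAP*

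**What the plan says.** SAP 6.3.2.2 (Risk periods) starts time at risk on the first day of challenge. It ends it as follows: "Time at risk will be censored on protocol visit D314 (28 days post challenge), drop-out date, start date of antimalarial treatment" or the date of meeting an endpoint, whichever is earliest. The duration formula starts from the same date ("Time at risk will be calculated as: censor date", minus the challenge date, plus one) and does not refer to a slide.

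The event in SAP 6.3.2.1 is asexual blood-stage "parasite density > 0 detected by blood slide reading". The slide schedule in protocol section 3 "will be collected daily for 14 days (from Day 291 [Visit 12] to Day 304 [Visit 25]) and then every two days" up to Day 314. In post-challenge time that is Days 5 to 18 daily, then Days 20, 22, 24, 26 and 28.

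The SAP does not define the drop-out date. The nearest wording is in protocol 10.2.1, where a subject has withdrawn when, among other things, "no further information has been collected for this subject from the date of withdrawal/last contact". Two statements in protocol 6.4.1.5 show that contact need not include a slide: "Telephone contact will be made if the subject does not keep a scheduled follow-up appointment", and "Symptom screening via telephone may suffice in lieu of clinical visits for Days 306, 308, 310, or 312 which fall upon a weekend".

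The second paragraph of SAP 6.3.2.2 deals with the relative-risk analysis separately. It neither censors nor removes per-protocol subjects who do not complete post-challenge follow-up.

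**The concern.** The event is detected only at a visit where blood is taken. After the last slide an infection cannot be recorded until another slide is read. If the drop-out date is later than the last slide, the subject sits in the Kaplan-Meier and log-rank risk sets for days on which an event was unobservable. A larger risk set makes each observed infection count for less, so the group's infection curve is too low.

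The time-to-onset comparisons with controls and with AduFx are at stake. They are secondary endpoints, but both tables are marked for web disclosure in SAP 12.2. With about 20 challenged subjects per group, one leaver is 1/20 = 5% of an arm. Time to onset against AduFx is also the comparison with the least room for such a shift, since the protocol's own power for schedule-to-schedule differences on the binary endpoint is 27% to 74%.

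**Working it through.** **Inputs from the documents.** At least 20 challenged per group, with 19/20 controls and 6/20 vaccinees infected (protocol 11.4). Pre-patent period in controls 7 to 18 days (protocol 6.4.1.5). Two-sided 5% tests (SAP 6.3.1).

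**Assumed, because the documents are silent.** The number of subjects lost after challenge, the gap between last slide and drop-out date, and the individual onset days. The 20% drop-out allowance in protocol 11.4 covers losses before challenge and cannot be used here.

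**The plan's own figure.** 1 − (6/20)/(19/20) = 1 − 0.300/0.950 = 68.4%, matching the stated 68%. The exact two-sided Fisher test at 20 per arm has power 99.7%, against the stated 99%. Both use the binary endpoint and do not depend on the censoring rule.

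**Vaccinees leave, long gap.** Let the six infections fall on Days 10 to 16, with 1, 2 or 3 uninfected vaccinees last smeared on Day 9 and last contacted on Day 20. Under the written rule they stay at risk past the last event, so the estimate is 6/20 = 30.0%. Censored at the last slide, they leave before the first event:

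| Leavers | Infection estimate | 1 − estimate/0.95 |
|---|---|---|
| 1 | 6/19 = 31.6% | 66.8% |
| 2 | 6/18 = 33.3% | 64.9% |
| 3 | 6/17 = 35.3% | 62.8% |

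The last column is only a yardstick. The SAP derives no efficacy estimate from Kaplan-Meier.

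**Vaccinees leave, scheduled gap.** With assumed vaccinee onsets on Days 11 to 18, one leaver and a 1-day gap move the yardstick from 67.0% to 66.8%. Two leavers with 2-day gaps move it from 66.4% to 65.4%.

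**Controls leave.** With assumed control onsets on Days 9 to 15, let the one uninfected control leave with a 10-day gap spanning them. The written rule gives 19/20 = 95% and last-slide censoring 19/19 = 100%. The yardstick goes from 1 − 0.30/0.95 = 68.4% to 1 − 0.30/1.00 = 70.0%, so here the written rule understates protection. With two leavers in each arm and 10-day gaps (18 controls infected), it is 1 − 0.300/0.900 = 66.7% as written and 1 − 0.333/1.000 = 66.7% after the change.

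The log-rank p-value against controls is below 0.00001 under both rules in every case run.

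**Against AduFx.** Assume 5/20 infected in AduFx (Days 11, 12, 13, 14, 16) and 10/20 in an alternative schedule (Days 10, 11, 11, 12, 12, 13, 13, 14, 15, 17), with two uninfected leavers. Without leavers, log-rank p = 0.097.

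| Leavers in | Last slide / drop-out | Their arm's estimate, as written → last slide | p, as written → last slide |
|---|---|---|---|
| AduFx | Day 10 / 12 | 26.9% → 27.8% | 0.128 → 0.151 |
| Alternative | Day 10 / 12 | 53.8% → 55.3% | 0.065 → 0.052 |
| AduFx | Day 8 / 18 | 25.0% → 27.8% | 0.097 → 0.155 |
| Alternative | Day 8 / 18 | 50.0% → 55.6% | 0.097 → 0.050 |

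First row by hand. As written, two events occur among 20, two leave, and three events occur among the remaining 16: 1 − (18/20)(13/16) = 26.9%. With last-slide censoring, both leave before the first event: 5/18 = 27.8%. In every row the leavers' own arm has the lower infection estimate under the written rule, while p moves up or down depending on the arm.

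**The case against.** The strongest objection is that planned follow-up leaves little room for a gap. Slides are daily through post-challenge Day 18, subjects sleep at the hotel from Day 9 with staff present round the clock, and, if required, "the investigators will physically locate and treat any malaria-infected subject who is unable to maintain the follow-up dictated by this study". Telephone screening in place of a visit is allowed only on Days 20 to 26, after the 7-to-18-day control range. A subject last smeared on Day 8 or 9 and last contacted on Day 18 or 20 would have missed essentially the whole hotel phase while still in contact. This stands: the 10-day cases are illustrations, not expectations.

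Second, reading the drop-out date as the last-contact date is an inference. Protocol 10.2.1 describes withdrawal from the study in general and does not use the SAP's term. A reader could take it to be the last attended visit, which would usually leave no gap. That also stands, but an undefined censoring date in a pre-specified analysis itself needs settling.

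Third, a reader might infer that the rule overstates protection. The documents do not support that. The rule applies to every arm; the control example reverses the sign, and against AduFx there is no fixed direction.

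Fourth, a reader might infer that reported vaccine efficacy would change. It would not: SAP 6.3.1 defines efficacy from the relative risk, which is uncensored, and the time-to-onset templates give summary statistics, a p-value and a curve. These analyses are secondary, and SAP section 7 calls all analyses descriptive.

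The per-protocol definition does not dispose of the point. Visits outside the allowed windows mean only that a subject may be ineligible, and SAP 6.3.2.2 itself provides for per-protocol subjects with incomplete follow-up.

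**Conclusion.** The point holds in a limited form. The written rule can count unobservable days as event-free, and where it does so around the days on which infections occur it lowers the Kaplan-Meier infection estimate of the group with post-challenge drop-outs. The effect on a comparison depends on who leaves: protection looks higher if vaccinees leave, lower if controls leave, and either is possible against AduFx. A general claim of overstated protection is not supported.

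For 1-to-2-day gaps in vaccinees, the size is about 0.2 to 1 percentage point on the efficacy yardstick. Two vaccinees with 10-day gaps give 68.4% to 64.9%, about 3.5 points. Conclusions against controls are not at risk in any case run. In a borderline comparison with AduFx, the censoring convention can move p by several hundredths, for example from 0.097 to the edge of 0.05. All these sizes rest on assumed losses, gaps and onset days. If nobody is lost after challenge and the Visit 30 slides are taken, nothing changes.

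This is a cheap improvement, not a threat to the primary result.

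**What to change.** In SAP 6.3.2.2, replace the drop-out date with the date of the last negative blood slide up to Visit 30, for every subject without a positive slide. Add that a challenged subject with no post-challenge slide is censored on the day of challenge. This case needs its own rule because slides start only on post-challenge Day 5. Leave the other terminating dates as they are.

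The cost is one sentence of SAP text and one derived variable. Protocol Tables 6 to 8 already mark the smears for eCRF documentation, so no new data are needed. The downside is slightly changed time-to-onset estimates, in either direction, if any subject is lost after challenge.

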6.4.1.5. Management of infected human subjects

The pre-patent period for *P. falciparum* in man normally averages 9-12 days. In previous studies, the pre-patent period in controls varied from 7-18 days. The shortest reported pre-patent period in man is five days, and the longest is 25 days [Ballou, 1987]. An immunized individual who does not have complete protection may have a prolongation of the parasite pre-patent period.

Beginning on Day 5 (Day 291 [Visit 12]) after their challenge, subjects will be seen and evaluated daily by a study investigator and blood will be drawn for blood smears to check for the presence of parasites as described in Section 6.4.1.4. If fever or symptoms develop at any time, blood smears will be done more frequently (every 6 to 12 hours), and a study investigator will evaluate the subject. A confirmed positive result will be relayed immediately to the on-call investigator/study personnel by the microscopists. The infection will be treated early (i.e. as soon as parasites can be identified on thick smear) according to the treatment regimen outlined in Section 6.4.1.6.

Beginning on Day 9 post-challenge (Day 295 [Visit 16]), a group of hotel rooms in the local area of WRAIR, will be reserved for malaria-challenged subjects. The subjects will be required to spend their nights there to allow for more rapid assessment of any potential symptoms of malaria during the hours that the study centers are closed. There will be an investigator present on-site and available for subject assessment. There will also be qualified study personnel on site 24 hours per day during the hotel phase of the study.

A blood sample for assessment of parasitemia (PCR testing) will be collected on the day of subject entry into the hotel phase (Day 295 [Visit 16]) to provide the study team an estimate of the number of subjects likely to develop malaria within the first few days of the hotel phase. This will allow the principal investigator and the study team to maximize subject safety by properly allocating resources and medical personnel to meet any high demand periods (i.e. periods when a large number of subjects are/will become ill). These samples will be processed by and assessed at WRAIR.

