Visit 2 → Visit 3 (2 nd vaccination)	28 days	± 7 days
Visit 3 → Visit 5	7 days	± 1 day
Visit 3 → Visit 6	30 days	± 7 days
Visit 3 → Visit 7 (3 rd vaccination)	168 days	± 14 days
Visit 7 → Visit 9	7 days	± 1 day
Visit 7 → Visit 10	30 days	± 7 days
Visit 7 → Visit 11 (Challenge)	90 days	+ 14 days
Visit 11 → Visit 30	28 days	± 7 days
Visit 30 → Visit 31	62 days	± 14 days

¹ Whenever possible the investigator should arrange study visits within this interval.

² Subjects may not be eligible for inclusion in the according-to-protocol (ATP) cohort for analysis of immunogenicity and efficacy if they make the study visit outside this interval.

Table 10 Intervals between study visits for the investigational vaccine groups: Adu1Fx

Interval	Optimal length of interval ¹	Allowed interval ²
Visit 1 (Screening) → Visit 2 (1 st vaccination)	0 to 90 days	-
Visit 2 → Visit 7 (2 nd vaccination)	196 days	± 14 days
Visit 7 → Visit 9	7 days	± 1 day
Visit 7 → Visit 10	30 days	± 7 days
Visit 7 → Visit 11 (Challenge)	90 days	+ 14 days
Visit 11 → Visit 30	28 days	± 7 days
Visit 30 → Visit 31	62 days	± 14 days

¹ Whenever possible the investigator should arrange study visits within this interval.

² Subjects may not be eligible for inclusion in the ATP cohort for analysis of immunogenicity and efficacy if they make the study visit outside this interval.

Table 11 Intervals between study visits for the infectivity control group

Interval	Optimal length of interval ¹	Allowed interval ²
Visit 1b (Screening) → Visit 11 (Challenge)	0 to 56 days	-
Visit 11 → Visit 30	28 days	± 7 days

¹ Whenever possible the investigator should arrange study visits within this interval.

² Subjects may not be eligible for inclusion in the ATP cohort for analysis of immunogenicity and efficacy if they make the study visit outside this interval.

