11.4. Determination of sample size

The target enrollment for this study will be approximately 150 subjects (26 subjects per vaccine group and between 20 and 30 subjects in the infectivity control group) to ensure at least 20 subjects in each group will undergo sporozoite challenge, given an approximate 20% estimated drop-out rate in vaccinees, based on past experience.

Assuming at least 19/20 controls and 6/20 vaccinees become positive (vaccine efficacy approximately 68%) the trial has 99% power to detect statistically significant vaccine efficacy of each of the vaccination groups over the infectivity controls for an overall power of 96% for the primary endpoint (p-value < 0.05).

For secondary efficacy endpoints the power of the trial to detect incremental vaccine efficacy of one schedule over any other is presented below:

Vaccine efficacy group x over controls	Vaccine efficacy group y over controls	Incremental Vaccine efficacy of group y over x	Power
50%	75%	50%	27%
50%	80%	60%	41%
50%	85%	70%	57%
50%	90%	80%	74%

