Visit 1b (Screening) → Visit 11 (Challenge)	0 to 56 days	-
Visit 11 → Visit 30	28 days	± 7 days

¹ Whenever possible the investigator should arrange study visits within this interval.

² Subjects may not be eligible for inclusion in the ATP cohort for analysis of immunogenicity and efficacy if they make the study visit outside this interval.

The following group names will be used for the statistical analyses:

Group order in tables	Group label in tables	Group definition for footnote
1	AduFx	RTS,S/AS01 _B full dose administered at Month 0, Month 1 and RTS,S/AS01 _B 1/5 th dose administered at Month 7
2	2PedFx	RTS,S/AS01 _E double dose administered at Month 0, Month 1 and double dose RTS,S/AS01 _E 1/5 th dose administered at Month 7
3	PedFx	RTS,S/AS01 _E full dose administered at Month 0, Month 1 and RTS,S/AS01 _E 1/5 th dose administered at Month 7
4	Adu2Fx	RTS,S/AS01 _B full dose at Month 0 and RTS,S/AS01 _B 1/5 th dose administered at Month 1, Month 7
4	Adu1Fx	RTS,S/AS01 _B full dose at Month 0 and RTS,S/AS01 _B 1/5 th dose administered at Month 7
5	Control	Subjects will not receive any immunization but will undergo sporozoite challenge

Two defined pooled groups:

Group order in tables	Group label in tables	Group definition for footnote
1	P	All subjects who have not been infected by P. falciparum parasitemia (defined by a positive blood slide) during the challenge and were part of one of the vaccinated groups
2	NP	All subjects who have been infected by P. falciparum parasitemia (defined by a positive blood slide) during the challenge and were part of one of the vaccinated groups

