6.3. Efficacy analysis

6.3.1. Analysis of efficacy planned in the protocol

The analysis of efficacy will be performed on the PPS for analysis of immunogenicity and efficacy.

Efficacy will be assessed by comparison of *P. falciparum* parasitemia incidence and time to onset of *P. falciparum* parasitemia after sporozoite challenge.

Vaccine efficacy (VE) is defined as $100 \times (1 - \text{Relative Risk})$. Relative risk of infection and 95% CI will be calculated.

Fisher's Exact test will be used for the comparison of *P. falciparum* parasitemia incidence after challenge between each one of the vaccine groups (AduFx, 2PedFx, PedFx, Adu2Fx, and Adu1Fx) and the infectivity control group.

Kaplan-Meier analysis will be performed on time to onset of *P. falciparum* parasitemia, for comparisons between each one of the vaccine groups (AduFx, 2PedFx, PedFx, Adu2Fx, and Adu1Fx) and the infectivity control group, using the log-rank statistic.

The same methodology will be applied for the evaluation of the vaccinated groups versus the immunization schedule of reference (AduFx group).

All statistical tests will be two-tailed at 5% significance level.

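### The primary relative risk counts anyone who leaves before Day 28 without a positive slide as uninfected, which can inflate vaccine efficacy if late infections are missed mainly in vaccinees

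*SAP*

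**What the plan says.** - **Relative risk.** SAP 6.3.2.2 treats all subjects in the per-protocol set (PPS) as at risk, and "no censoring or elimination will be applied for subjects not completing the entire protocol defined post challenge follow-up". Under SAP 6.3.2.1 a case requires a positive blood slide.
- **Time to onset.** The same section censors at drop-out, at the 28-day visit, at the start of antimalarial treatment or at the endpoint, whichever comes first.
- **Protected group.** SAP section 2 opens the definition of group P with "All subjects who have not been infected by" *P. falciparum*, judged by slide, and limits it to vaccinees. It sets no minimum follow-up. Group P feeds the protected versus not-protected (P/NP) comparisons and the logistic models of SAP 6.4.2.
- **Visit window.** Protocol 6.5, Tables 9 to 11, repeated in SAP section 2, allows the interval "Visit 11 → Visit 30" to be 28 days plus or minus 7.
- **Slide schedule.** Protocol 6.4.1.5 requires subjects without malaria to give slides every two days up to Day 28 after challenge. Telephone screening may replace the Day 20, 22, 24 and 26 visits when they fall on a weekend.
- **Timing of patency.** The same section gives a pre-patent period of 7 to 18 days in past controls. It adds: "The shortest reported pre-patent period in man is five days, and the longest is 25 days". On vaccinees it says: "An immunized individual who does not have complete protection may have a prolongation of the parasite pre-patent period".
- **Provisions that pull the other way.** Elimination code 2090 (SAP 5.2.3.1) removes from the PPS subjects who did not keep the blood sampling schedule of SAP Tables 1 to 3, which include Visit 30. Template 11 (SAP 12.6.2) takes its N without missing values. Code 2090 is not among the codes for the Adapted PPS (SAP 5.2.4.1).

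No sensitivity analysis for incomplete post-challenge follow-up is planned.

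**The concern.** A subject who leaves with no positive slide has an unknown Day-28 outcome. The relative-risk rule records that outcome as no infection, while the Kaplan-Meier analysis in the same section treats it as unknown.

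The rule covers both arms, but the infections it can hide need not be balanced. Past controls were patent by Day 18, whereas a partly protected vaccinee may be later. Losses after about Day 18 would therefore tend to hide vaccinee infections more than control infections.

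Four results are exposed: the VE estimates against controls; the comparisons with AduFx, which use the same method (SAP 6.3.1); the P/NP analyses, where some vaccinees labelled protected may not be; and the interim VE on the Adapted PPS, which informs the booster choice for study Malaria-102 (SAP 8.1).

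**Working it through.** **Inputs.** Planned attack rates are 19/20 controls and 6/20 vaccinees (Protocol 11.4). VE = 1 − relative risk, with a two-sided 5% Fisher test (SAP 6.3.1). The 20% drop-out in Protocol 11.4 takes 26 enrolled to at least 20 challenged, so it falls before challenge. No post-challenge loss rate is given, so the numbers of leavers below are assumptions.

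**The plan's own figures.** VE = 1 − (6/20)/(19/20) = 1 − 0.30/0.95 = 68.4%, against approximately 68% stated. The log-relative-risk 95% CI is 37.9% to 84.0%. Exact power of the two-sided Fisher test with 20 per arm is 99.7%, against 99% stated. Both reproduce.

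**1. Masked infections.** Suppose the true results are 6/20 and 19/20, and some infections are never seen because the subject left first.

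| Masked infections | VE reported |
|---|---|
| none | 68.4% |
| 1 vaccinee | 1 − (5/20)/(19/20) = 73.7% |
| 2 vaccinees | 1 − (4/20)/(19/20) = 78.9% |
| 1 control | 1 − (6/20)/(18/20) = 66.7% |
| 2 controls | 1 − (6/20)/(17/20) = 64.7% |

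Each masked vaccinee infection adds 0.05/0.95 = 5.3 points. The first masked control infection subtracts 68.4 − 66.7, about 1.8 points before rounding.

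**2. Direction.** If a share f of infections is masked in both arms, VE = 1 − 0.30(1 − f)/[0.95(1 − f)]. The factor cancels and VE stays at 68.4%. If only vaccinee infections are masked, VE = 1 − 0.30(1 − f)/0.95. That gives 70.0%, 71.6% and 74.7% for f = 5%, 10% and 20%.

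**3. Leavers whose outcome is unknown.** Observed results are 6/20 and 19/20, and k of the 14 slide-negative vaccinees left early.

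| k | SAP 6.3.2.2 | leavers excluded | leavers counted infected |
|---|---|---|---|
| 1 | 68.4% | 1 − (6/19)/0.95 = 66.8% | 1 − (7/20)/0.95 = 63.2% |
| 2 | 68.4% | 1 − (6/18)/0.95 = 64.9% | 1 − (8/20)/0.95 = 57.9% |

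For k = 2, a Kaplan-Meier Day-28 VE lies between 64.9% (both lost before any infection appears) and 68.4% (both lost after the last one). With no losses it equals the planned estimate.

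**4. Significance.** With up to four vaccinee leavers counted as infected, the Fisher p-value against controls is at most 0.0033. With up to three control infections masked it is at most 0.0037.

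**5. Window against schedule.** 28 − 7 = Day 21, which is Study Day 286 + 21 = 307. That precedes the slides due on Days 22, 24 and 26 (Study Days 308, 310 and 312) and the longest reported pre-patent period of 25 days. Tables 9 to 11 therefore accept a Visit 30 date that the slide schedule does not.

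**The case against.** Several points on the other side are sound.

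- **The rule is arm-neutral.** A reader might infer that it necessarily inflates VE. It does not: step 2 shows no change under equal proportional masking, and masked control infections lower VE.
- **The window does not permit slides to stop at Day 21.** A reader might take a subject whose last slide is on Day 21 as fully compliant. The two-day slide schedule in Protocol 6.4.1.5 runs to Day 28 regardless, so this is an unreconciled conflict. Nor does the protocol report patency after Day 25; it says only that prolongation is possible in vaccinees.
- **Losses should be few.** There are daily visits from Day 5, a hotel stay from Day 9 to Day 18, telephone contact after missed visits, and an undertaking to find infected subjects who cannot keep up follow-up.
- **Code 2090 and Template 11 may remove some leavers.** A subject with no Visit 30 could be taken out of the PPS before the rule applies. This does not settle the matter. Section 6.3.2.2 expressly rules out elimination for incomplete follow-up, and a Visit 30 on Day 21 satisfies Tables 1 to 3. For one lost vaccinee the readings give either 6/20 (68.4%) or 6/19 (66.8%), so the primary denominator is not uniquely defined. The Adapted PPS has no code 2090.
- **The censored analysis and a cumulative-incidence figure are already planned.** They are a partial check, but no VE is derived from them.

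**Conclusion.** The rule is explicit, and it turns an unknown outcome into a non-event. It can overstate VE, on the condition that late infections are missed proportionally more often in vaccinees. The timing information in Protocol 6.4.1.5 makes that plausible after about Day 18 but does not establish it.

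On the planning figures the sensitivity is about 5.3 points up per masked vaccinee infection and about 1.8 points down for the first masked control infection. These are per missed infection. It would be tempting to read one or two leavers per arm as 5 to 10 points of bias, but that assumes every leaver was infected. A single vaccinee leaver puts VE between 63.2% and 68.4%, depending on the unknown outcome.

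The real size cannot be stated because no post-challenge loss rate is given. Significance against controls held in every scenario run. The exposed results are the VE estimates themselves, the comparisons with AduFx (where Protocol 11.4 gives power of only 27% to 74% between schedules), the P/NP classification and the interim VE.

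**What to change.** 1. Report VE as 1 minus the ratio of Kaplan-Meier Day-28 risks, at least as a pre-specified sensitivity analysis.
2. Add a worst-case table that counts incompletely followed vaccinees as infected and incompletely followed controls as uninfected. Produce both for the PPS and for the Adapted PPS used at the interim.
3. State in the SAP what counts as complete follow-up for the slide endpoint. In the P/NP analyses, classify slide-negative vaccinees without it as unknown.
4. Reconcile SAP 6.3.2.2 with code 2090 and with the N of Template 11, so that the primary denominator has one definition.
5. Reconcile the Visit 30 window in Protocol 6.5 and SAP section 2 with the slide schedule in Protocol 6.4.1.5.

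The cost is SAP wording and a little more analysis work. If anyone is lost, the reported VE may be slightly less favourable.
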